11.1. Adverse Events

Adverse events will be summarized by SOC and PT for the Safety Set. TEAEs are defined as AEs which commence on or after the first administration of the study drug, or those that occur before first study drug administration but worsen in frequency or severity after first study drug administration. All other AEs are considered PTAE.

TEAEs and PTAEs will be included in the summary tables; separate listings for TEAEs and PTAEs will be produced. Additional listings will be provided for deaths, SAEs, TEAEs leading to study drug withdrawal, TEAEs considered MAVE, and TEAEs of special interest.

Meningococcal infections will be collected as TEAEs of special interest. In addition, a medical review will be done to ensure that no relevant events were missed.

If the relationship to study drug is missing for TEAEs, then the relationship will be counted as related to study product for the summary tables. Missing severity for TEAEs will be counted as Grade 3.

Tables will be sorted by descending frequency of SOC and by descending frequency of PT within SOC, based on MedDRA version 23.1. Participants having multiple AEs within a category (eg, overall, SOC, PT) will be counted once in that category. For severity/relationship tables, the participant's highest grade/most related event within a category will be counted. Percentages will be based on the number of participants in the Safety Set.

An overall summary table of TEAEs will be presented using summary statistics (n, %). The number of events (n) and number of participants with events (n, %) will be displayed for the following events subcategories:

The following tables will be provided:

- An overall summary of the number and percentage of participants reporting TEAEs, treatmentemergent SAEs (TESAEs), TEAEs leading to death, TEAEs leading to withdrawal of study drug, TEAEs by maximum relationship, TESAEs by maximum relationship, TEAEs by maximum Common Terminology Criteria for Adverse Events (CTCAE) grade, TEAEs considered MAVE, TEAEs of special interest, and TEAEs related to COVID-19 infection
- PTAEs overall and by SOC and PT;
- TEAEs overall and by SOC and PT;
- TEAEs by maximum CTCAE grade, overall and by SOC and PT;
- TEAEs related to study drug, overall and by SOC and PT;
- TESAEs overall and by SOC and PT;
- TESAE related to study drug, overall and by SOC and PT;
- TEAEs considered MAVE, overall and by SOC and PT.

This document is confidential.

SAP Version: 2.0 09-Feb-2023

Controlled Document ID: 3903A.02, Effective Date 31-Aug-2020

Sponsor: Alexion Pharmaceuticals, Inc. Protocol No.: ALXN1210-PNH-401

- TEAEs of special interest, by SOC and PT.
- TEAEs related to COVID-19, overall and by SOC and PT.

11.2. Laboratory Evaluations

Safety laboratory samples for hematology, chemistry, urinalysis, and coagulation will be collected by both central and local laboratory at timepoints specified in the schedule of assessments (see sections 1.3 and 10.2 of the protocol).

Descriptive statistics by visit will be presented for each central laboratory parameter and for changes from baseline (continuous variables), for the Safety set. Shift tables over time will be presented for all central laboratory values, where applicable, using normal, low, or high on the basis of normal range values. Individual participant plots as well as boxplots will be presented for the following central laboratory parameters: hemoglobin, haptoglobin, hematocrit, reticulocytes, LDH, bilirubin, direct bilirubin, creatinine, aspartate aminotransferase, alanine aminotransferase, and gamma-glutamyl transferase.

Furthermore, results of PNH clone during the course of the study will be summarized.

Clinical central laboratory samples that meet the definition of table top hemolysis (TTH) will be identified and all potassium, alanine aminotransferase, aspartate aminotransferase, magnesium, phosphorous, and LDH samples affected by TTH will be excluded from analysis of all efficacy and safety endpoints, with the exception that the LDH values will be used for the qualification of BTH. The TTH samples from the central laboratory will be defined as having serum potassium ≥ 6 mmol/L and LDH $\geq 2 \times$ ULN, and will be listed.

All central and local laboratory data will be presented in by-participant listings.

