#### 2.3.1. Risk Assessment

Risks of Clinical Significance	Summary of Data/ Rationale for Risk	Mitigation Strategy
Potential Risks		
Serious hemolysis after drug discontinuation	This potential disease-associated risk is based on a theoretical possibility, associated with abrupt ravulizumab discontinuation, resulting in a so- called rebound effect. Rebound effect is described for many biologicals but has not been observed in ravulizumab clinical trials.	The effects are most likely not completely preventable, but their severity can be minimized by avoiding abrupt drug discontinuation. Participants who discontinue the drug will be followed up for 16 weeks if participants remain in the study.
Serious infection	This potential risk is a based on the mode of action of ravulizumab and experience with the use of eculizumab. Since the relevance of serious infection with ravulizumab therapy has not been confirmed in clinical trials, this remains a potential risk.	Increased awareness of healthcare professionals and participant about the potential risk of serious Infection. Monitoring for signs and symptoms of serious infections will be conducted as part of routine safety assessments for this study.
Malignancies and hematologic abnormalities	The natural evolution of PNH disease makes PNH patients more prone to development of hematologic abnormalities or malignancies as approximately 30-70% of PNH patients eventually develop aplastic anemia or myelodysplastic syndrome. The potential role of ravulizumab in the risk of such abnormalities or malignancies (if any) is unknown	Monitoring as part of routine safety assessments for this study.
Immunogenicity	Treatment with any therapeutic protein has the potential to induce an immune response. Potential clinical consequences may include severe hypersensitivity type reactions, decrease in efficacy and induction of autoimmunity, including antibodies to the endogenous form of the protein (Casadevall, 2002; Li, 2001). Protein therapies administered IV have the potential risk of causing local (infusion-site reactions) and systemic reactions (infusion-associated reactions).	In the ALXN1210-PNH-103 and ALXN1210-PNH-201 studies, no participants have returned a positive ADA sample. ADA will be assessed. Monitoring for infusion reactions will be conducted as part of routine safety assessments for this study.

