### **Diagnostic Assessments**

- 19. More than one LDH value  $> 2 \times$  ULN within the 6 months prior to Day 1.
- 20. Platelet count <  $30,000/\text{mm}^3$  ( $30 \times 10^9/\text{L}$ ) at Screening.
- 21. Absolute neutrophil count  $< 500/\mu L (0.5 \times 10^9/L)$  at Screening.
- 22. Positive human immunodeficiency virus (HIV) antibody test.

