#### Assessment of Intensity

The Investigator will make an assessment of intensity for each AE and SAE reported during the study and assign it to 1 of the following categories from National Cancer Institute CTCAE v5.0, published 27 Nov 2017:

- Grade 1: Mild (awareness of sign or symptom, but easily tolerated)
- Grade 2: Moderate (discomfort sufficient to cause interference with normal activities)
- Grade 3: Severe (incapacitating, with inability to perform normal activities)
- Grade 4: Life-threatening
- Grade 5: Fatal

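### The SAP 11.2 shift tables cannot show a further platelet or neutrophil fall in participants already below normal at entry, and no other laboratory summary counts such falls

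*SAP*

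**What the plan says.** SAP 11.2 plans four kinds of laboratory output.

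- **Shift tables.** "Shift tables over time will be presented for all central laboratory values, where applicable, using normal, low, or high". The bands are set by the reference limits, and no grade, threshold or worst-value category is added.
- **By-visit summaries.** "Descriptive statistics by visit will be presented for each central laboratory parameter and for changes from baseline (continuous variables), for the Safety set". SAP 6.1 defines these as n, mean, SD, median, minimum and maximum.
- **Individual plots and boxplots** for eleven named parameters. Hemoglobin is on the list; platelets and neutrophils are not.
- **By-participant listings** of all central and local results.

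Protocol 5.2 excludes a platelet count below 30 x 10^9/L (exclusion 20) and an absolute neutrophil count below 0.5 x 10^9/L (exclusion 21) at Screening. It sets no requirement that either count be normal.

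Protocol 2.3.1 lists malignancies and hematologic abnormalities as a potential risk. It notes that "approximately 30-70% of PNH patients eventually develop aplastic anemia or myelodysplastic syndrome" and calls the drug's role, if any, unknown. The stated mitigation is "Monitoring as part of routine safety assessments for this study".

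**The concern.** A three-category table registers a fall only when a value crosses a limit of the normal range. A participant who starts low has no lower category to move into. The entry criteria allow such a start for the two counts that bear most directly on marrow failure, and the protocol relies on routine safety data to watch for it.

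The risk is one of reading. A platelet or neutrophil shift table with nothing off the diagonal could be taken to mean that counts held steady, when some participants who were already low had fallen further. No estimate, interval or efficacy conclusion is affected.

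**Working it through.** **Inputs.** Entry floors of 30 and 0.5 x 10^9/L (Protocol 5.2); three shift categories (SAP 11.2); about 20 participants (SAP 3.3). The documents give no reference ranges, so the lower limit of normal (LLN) is assumed: 130-150 for platelets and 1.5-2.0 for neutrophils, both x 10^9/L. The plan states no figure for the shift tables, so there is none to reproduce.

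**Step 1: width of the low band open at entry.** Floor divided by LLN.

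- Platelets: 30/150 = 20% to 30/130 = 23%.
- Neutrophils: 0.5/2.0 = 25% to 0.5/1.5 = 33%.

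A participant may therefore enter at a fifth to a third of the lower limit.

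**Step 2: hypothetical falls put through the SAP categories.**

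| Analyte (x 10^9/L) | Baseline to later | Relative change | LLNs tried | Cell |
|---|---|---|---|---|
| Platelets | 60 to 20 | -40/60 = -67% | 130, 140, 150 | low to low at all |
| Platelets | 100 to 25 | -75/100 = -75% | 130, 140, 150 | low to low at all |
| Platelets | 145 to 10 | -135/145 = -93% | 130, 140, 150 | normal to low at 130 and 140; low to low at 150 |
| Neutrophils | 1.0 to 0.3 | -0.7/1.0 = -70% | 1.5, 1.8, 2.0 | low to low at all |
| Neutrophils | 1.4 to 0.4 | -1.0/1.4 = -71% | 1.5, 1.8, 2.0 | low to low at all |

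The third row shows that the same fall can register or not depending only on the laboratory's limit.

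**Step 3: what the by-visit change summary adds.** One participant falling from 60 to 20 among 20 moves the mean by -40/20 = -2.0; a neutrophil fall from 1.0 to 0.3 moves it by -0.7/20 = -0.035. The minimum change would print -40 if that were the largest fall. It would also print -40 if five participants each fell by 40. The minimum shows the worst case at that visit but not how many participants worsened.

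**Step 4: worst values.** Under SAP 6.4, when several records share a visit window, the one nearest the window midpoint is analyzed. The Day 71 window runs from 43 to 98, midpoint (43 + 98)/2 = 70.5. A scheduled sample on Day 71 (0.5 days away) displaces an unscheduled one on, say, Day 55 (15.5 days away), even if Day 55 held the lowest count. SAP 11.2 plans no summary of the worst post-baseline value.

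**Step 5: does banding within low help?** Take only the protocol's own entry floors as extra cut-points. Platelets 60 to 20 then move from the 30-to-LLN band to below 30, and neutrophils 1.0 to 0.3 move from the 0.5-to-LLN band to below 0.5. Both become visible.

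**The case against.** The strongest reply is that the shift table is one output among several. Much of that stands.

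- **Hemoglobin is covered.** A fall of 2 g/dL or more from the participant's own baseline is counted in the stabilized-hemoglobin endpoint with an exact interval (SAP 8.2.4), and hemoglobin is plotted individually. A reader might infer that most participants could lose 2 g/dL unseen; the SAP contradicts that.
- **Other categorical laboratory counts exist**: LDH at or below 1.0 and 1.5 x ULN (SAP 8.2.2) and free C5 at or above 0.5 µg/mL (SAP section 10). Neither concerns platelets or neutrophils.
- **Individual cases can surface.** The largest fall is printed as a minimum, and with about 20 participants the full listings can be read directly.
- **Adverse events.** Protocol 8.2.4 has the Investigator review each report and record clinically relevant changes as adverse events. SAP 11.1 tabulates treatment-emergent events by maximum CTCAE grade. A new malignancy or myelodysplastic syndrome could be reported there.

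A reader might therefore go too far in saying that the named hematologic risk does not register in this trial. The documents do not support that.

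The adverse-event route does not fully close the gap. Protocol 8.2.4 and 10.3 set aside laboratory findings tied to the underlying disease unless they are judged more severe than expected, and Protocol 2.3.1 itself links hematologic abnormalities to the natural course of PNH. Whether a falling count is reported thus rests on judgment, and only meningococcal infection is an event of special interest (Protocol 8.3.6).

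Two further points are fair. Protocol 9.4.2.2 asks only for shifts from baseline where applicable, which the SAP delivers. The table shells are a separate document that was not available, so they may already contain more.

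**Conclusion.** The point holds as a modest reporting gap confined to platelets and neutrophils. In the SAP 11.2 shift table, a participant low at baseline cannot show a further fall. Apart from falls that an Investigator reports as adverse events, no planned output counts such participants, none summarizes the worst post-baseline value, and neither analyte is among the individual plots or boxplots.

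The number affected cannot be stated. The exclusions set floors and say nothing about how many participants enter low. The cases in the working are hypothetical and rest on assumed lower limits; all but one read low to low across the whole assumed range.

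The plan is less thorough here than for ECG, where SAP 11.4 lists absolute QT and QTcF cut-offs (450, 480 and 500 msec) and increases from baseline (30 and 60 msec). The change is a cheap improvement and does not affect the primary analysis.

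**What to change.** In SAP 11.2, for platelet count and absolute neutrophil count in the Safety Set:

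1. Add a table of baseline CTCAE v5.0 grade against worst post-baseline grade. State that it uses all post-baseline central laboratory records, including unscheduled visits and records not selected under the SAP 6.4 window rule.
2. Write the numeric grade limits into the SAP, since neither document reproduces them. The protocol already uses this scale for adverse events, where the Investigator must "assign it to 1 of the following categories from National Cancer Institute CTCAE v5.0". If a simpler table is preferred, the entry floors of 30 and 0.5 x 10^9/L can serve as extra bands within low.
3. Add both analytes to the individual participant plots and boxplots.
4. Optionally extend the graded table to other gradable analytes. Keep low/normal/high for the rest.

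Platelet count and white-cell differential are already in Protocol Table 6, and hematology is scheduled on Day 1 and at every evaluation visit in Protocol Table 2, so no new data are needed. The cost is SAP wording, some programming, and one or two extra tables and figures. Sample size, conduct and endpoints do not change. The graded count would still be imprecise: 0 of 20 carries an exact 95% interval of 0% to 17% (SAP 3.3; recomputed as 0 to 16.8%).

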8.1. Primary Efficacy Endpoint and Analysis

The primary efficacy endpoint is the proportion of participants who experience free C5-associated BTH through Day 351.

BTH is defined as at least 1 new or worsening symptom or sign of intravascular hemolysis (fatigue, hemoglobinuria, abdominal pain, shortness of breath [dyspnea], anemia [hemoglobin < 10 g/dL], MAVE, including thrombosis, dysphagia, or erectile dysfunction) in the presence of elevated LDH, which is defined as LDH \geq 2 × ULN. The determination about whether a BTH has occurred will be reflected on the BTH form of the eCRF. In the event of a BTH outside the visit schedule, an unscheduled visit will occur, at which point all information pertaining to the BTH will be collected.

Free C5-associated BTH is defined as BTH concurrent with free C5 concentrations $\geq 0.5 \,\mu\text{g/mL}$. The first C5 concentration captured on or after the date of the BTH will be considered when defining a BTH event as free C5-associated.

The proportion of participants who experience free C5-associated BTH through Day 351 will be calculated along with a 2-sided exact 95% CI using the Clopper-Pearson method. All data will be listed.

Participants who withdraw from the study due to lack of efficacy during the Evaluation Period will be considered as non-responders and will be counted in the group with free C5 associated BTH if free C5 is ≥ 0.5 µg/mL at ET visit. For participants who withdraw from the study for any other reason during the Evaluation Period, their data up to the time of withdrawal will be used to assess free C5 associated BTH.

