8.2.2. Hemolysis

Hemolysis is analyzed as directly measured as the percentage change in LDH from baseline.

The percentage change in LDH will be analyzed using a mixed model for repeated measures (MMRM) (Mallinckrodt, 2001; Mallinckrodt, 2004) with the fixed categorical effects of study visit, and the continuous fixed covariate of baseline LDH. Baseline is defined as the average of all assessments analyzed by the central laboratory prior to the first study drug administration. The Kenward-Roger approximation will be used to estimate denominator degrees of freedom. A p-value testing whether percent changes differ from 0 at each visit will be calculated.

Absolute LDH levels, and the change and percent change from baseline, will be summarized at all study visits up to Day 351.

This document is confidential

SAP Version: 2.0 09-Feb-2023

Controlled Document ID: 3903A.02, Effective Date 31-Aug-2020

The number (%) of participants achieving LDH levels at or below ULN (1.0 × ULN) and levels at or below 1.5 × ULN will be displayed.

Mean (±95% CI) of absolute LDH levels, and the change and percent change from baseline will be plotted over time.

All data will be listed.

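### The table-top hemolysis rule can remove only high LDH values from the LDH endpoint, including one that qualified a BTH, and no analysis with those values included is planned

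*SAP*

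**What the plan says.** SAP 11.2 sets the rule. "The TTH samples from the central laboratory will be defined as having serum potassium ≥ 6 mmol/L and LDH" at or above 2 × ULN; both conditions must be met. For a flagged sample, potassium, ALT, AST, magnesium, phosphorus and LDH are "excluded from analysis of all efficacy and safety endpoints, with the exception that the LDH values will be used for the qualification of BTH". Flagged samples are listed, and "All central and local laboratory data will be presented in by-participant listings".

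SAP 8.2.2 covers the secondary endpoint that the rule touches: "Hemolysis is analyzed as directly measured as the percentage change in LDH from baseline". It specifies an MMRM with a test against zero at each visit, by-visit summaries, and the number of participants with LDH at or below 1.0 and 1.5 × ULN. It does not mention TTH.

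SAP 6.3.1 says that efficacy data are analysed as they stand, without imputation. Protocol 9.4.1 contains no TTH rule, and SAP Section 14 does not list one among the changes from the protocol. Neither document plans an LDH analysis with the flagged values included.

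**The concern.** An exclusion for specimen artefact is safest when it rests on something other than the outcome. Here the outcome is half of the definition. A sample with potassium of 6 mmol/L or more and LDH of 1.9 × ULN stays in; at 2.0 × ULN it goes. The cut-off is also the LDH criterion for breakthrough hemolysis (BTH) in SAP 8.1, so the values at risk of deletion lie in the range that signals hemolysis in this trial. The rule uses no further evidence, although Protocol 8.1.2 collects free hemoglobin, haptoglobin and reticulocytes.

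The result can be inconsistent within one participant: a reading may count towards a BTH and yet be absent from the endpoint that measures hemolysis directly. With a single arm of about 20 participants there is no comparator in which a one-sided deletion could cancel out, and one or two samples can move a visit mean.

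**Working it through.** **Inputs from the documents.** Flag: potassium ≥ 6 mmol/L and LDH ≥ 2 × ULN (SAP 11.2). Sample size about 20 (SAP 3.3). The denominator for percentages is participants with an observation (SAP 16.2.5.2). LDH baseline is the mean of central laboratory values before first dose (SAP 6.2). The documents state no TTH frequency and no expected effect of the rule, so there is no plan figure for the rule to reproduce. The one related figure, the exact interval for 15/20 in SAP 3.3 (51% to 91%), reproduces as 50.9% to 91.3%.

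**1. Shift in a raw visit mean.** Let x be the percent change of the dropped value and m the mean of the other 19.
- Mean with all 20: (19m + x)/20. Mean after the drop: m.
- The mean therefore falls by (x − m)/20.
- The percent change is x = (LDH/baseline − 1) × 100, with both in multiples of ULN.

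| LDH (× ULN) | Baseline (× ULN) | x | Fall if m = 0 | Fall if m = 20 |
|---|---|---|---|---|
| 2 | 1.25 | 60% | 3 points | 2 points |
| 2 | 1.0 | 100% | 5 points | 4 points |
| 3 | 1.25 | 140% | 7 points | 6 points |
| 3 | 1.0 | 200% | 10 points | 9 points |

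The baselines, the LDH values and m are assumptions. The 3 to 10 point range needs m near zero. It is not a floor: with baseline 1.5 × ULN, LDH 2 × ULN and m = 20, x is 33.3% and the fall is (33.3 − 20)/20 = 0.7 points. Two such values with m = 0 double the range to 6 to 20 points.

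**2. Threshold proportions.** A flagged value is at least 2 × ULN, so it fails both thresholds. If no other record fills the visit, deletion moves the proportion from a/20 to a/19: from 19/20 (95%) to 19/19 (100%), or from 15/20 (75%) to 15/19 (78.9%).

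**3. Why the MMRM does not repair this.** The model treats a missing value as predictable from the participant's observed values. Here the value is missing because it was itself high. The participant's other visits recover part of the loss at most.

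**4. Net direction.** One visit was simulated under assumptions that do not come from the documents: baseline LDH lognormal with median 1.1 × ULN and log-SD 0.2; within-person log-SD 0.15; an artefact multiplies LDH by 1.3 to 3.0 and always gives potassium ≥ 6; real hemolysis multiplies LDH by 1.5 to 3.5 and gives potassium ≥ 6 with probability q. Bias is measured against the artefact-free mean percent change.

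| Scenario | Bias under the SAP rule | Bias with no exclusion |
|---|---|---|
| q = 0; artefacts in 2–10%, real hemolysis in 0–10% | +0.3 to +2.3 points | +2.3 to +13.4 points |
| q = 0.1; artefacts in 0–10%, real hemolysis in 5–10% | −1.3 to +1.3 points | 0 to about +13.4 points |
| q = 0.5; artefacts in 0–10%, real hemolysis in 5–10% | −1.2 to −6.4 points | 0 to about +13.4 points |

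The sign depends on how often real hemolysis comes with high potassium and how common artefacts are. The documents give neither.

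**The case against.** The case for the rule is good. Artefactual hemolysis in the tube raises LDH and, left in, would bias percent change upward by more than the rule leaves behind when flags are true artefacts. The potassium condition is a real second requirement: a high LDH with potassium below 6 mmol/L stays in. Nothing in the documents says that true PNH hemolysis often brings potassium to 6. A flagged screening value would also be dropped from baseline, which lowers baseline and pushes percent change up. These points stand. A reader might infer that the rule biases LDH percent change low overall; the documents do not support that.

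A reader might also infer that real high values disappear from the report. They leave the models and summaries, but SAP 11.2 lists them. Nor does a flagged LDH prove a BTH: "BTH is defined as at least 1 new or worsening symptom or sign of intravascular hemolysis", with LDH as the accompanying condition, and the primary endpoint goes further: "Free C5-associated BTH is defined as BTH concurrent with free C5 concentrations" at or above 0.5 μg/mL. Keeping the flagged LDH for BTH can only add events, which is conservative, and the SAP does not say that it does so because the values may be real.

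The LDH endpoint could miss a BTH reading without this rule. From Day 71 the SAP 6.4 windows are 56 days wide and use one record, the one nearest the midpoint. An unscheduled sample may not be selected, or an unflagged record may take its place. The study is estimation only, and the threshold proportions are displays, not listed endpoints; a move from 75% to 79% is small beside an interval of 51% to 91%.

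What remains is that a listing does not correct a model estimate, and that uncertainty about direction is a reason to show both results.

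**Conclusion.** The point holds in a limited form. The rule is one-sided and depends on the outcome. It can remove from the LDH analyses a reading that qualified a BTH, and the MMRM cannot undo that. If a flagged post-baseline value is real, the LDH percent change and the proportions at or below 1.0 and 1.5 × ULN look better than they are. The size is (x − m)/20 per value in the raw mean, about 3 to 10 points under the assumptions above; the shift in the MMRM estimate will differ because it borrows from other visits. If all flags are artefacts, the rule helps. The net direction is unknown because the documents give no TTH frequency.

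Separately, SAP 11.2 and SAP 6.3.1 do not agree: one removes efficacy values, the other says that all are analysed as they stand. The primary endpoint does not lose events through this rule. This is a cheap improvement to a secondary analysis.

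**What to change.** In SAP 11.2 and 8.2.2:

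1. Keep the planned analysis, and beside it repeat the LDH MMRM and the two threshold proportions with all TTH-flagged values included, as a sensitivity analysis.
2. Add a run that retains only the flagged values that qualified a BTH. It carries its own selection, since a value is kept only when a symptom or sign was also recorded, so it supplements the all-values run and does not replace it.
3. Report the number of samples flagged by visit, screening included, and how many coincide with a BTH.
4. Reconcile the rule with SAP 6.3.1 and refer to it in SAP 8.2.2.

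The cost is SAP wording and one or two reruns on data already collected. The downside is that some artefactual values enter the all-values run, so it should be read as a check on dependence and not as the better estimate.
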